Adapting an Evidenced-based Weight Management Intervention and Testing Strategies to Increase Implementation in Community Mental Health Programs

January 8, 2025
NCT03454997

STUDY PROTOCOL

STRATEGIES TO INCREASE IMPLEMENTATION OF AN ADAPTED, EVIDENCE-BASED WEIGHT MANAGEMENT INTERVENTION IN COMMUNITY MENTAL HEALTH PROGRAMS: THE ACHIEVE IMPLEMENTATION AND DISSEMINATION PILOT TRIAL

IRB00247344 January 8, 2025

Version 1.0 – February 23, 2021

Version 1.4 1.8.2025

- Change in PI to [name], MHS due to original PI leaving JHSOM.

Changes from version 1.3-10.18.2022

- Adding interviews six-month post project completion for staff coaches and administration
- Adding in \$25 for both completion of focus group and for a six-month post project interview for coaches and peer leaders
- Adding in \$25 for completion of focus group for other staff

Changes from version 1.2-March 8, 2022

- Adding Perceived Usefulness (motivational interviewing avatar platform) survey to coach participant six-month follow-up data collection

Changes from version 1.1- December 13, 2021

- Added Avatar Motivational Interviewing (MI) satisfaction survey to the coach participant six month follow-up data collection

Changes from version 1.0

Version 1.1- September 23, 2021

- Modified consumer participants eligibility criteria for BMI from $\ge 30 \text{ kg/m}^2$ to $\ge 25 \text{ kg/m}^2$
- Increased flexibility of program delivery by changing the number of groups offered each week from 3 groups/week to a minimum of one group/week
- Modified the curriculum to allow for the inclusion of group exercise during in-person groups, if permitted by the sites' COVID-19 safety protocols
- Modified the curriculum to allow for virtual exercise groups facilitated by a trained peer leader and study team

Table of Contents

1. ABSTRACT.....

1. ABSTRACT

Prevalence of obesity is significantly elevated in people with serious mental illness (SMI)¹⁻³, and obesity is a leading cause of preventable death in this population directly through its effects on cardiovascular disease (CVD) and indirectly by contributing other CVD risk factors⁴⁻¹⁰. In general populations, behavioral weight-loss interventions have been demonstrated to improve CVD risk by reducing blood pressure and glucose, as well as improving lipid profiles¹¹. However, behavioral interventions targeting changes in diet, exercise and weight loss need to be tailored to the particular needs of people with SMI, such as memory impairment and limited executive function^{12,13}.

The NIMH-funded Achieving Healthy Lifestyles in Psychiatric Rehabilitation (ACHIEVE) trial tested a behavioral weight-loss intervention for consumers with SMI who attended community-based psychiatric rehabilitation programs¹⁴. This randomized controlled trial (RCT) demonstrated clinically significant weight loss (mean 7 lbs. at 18 months)¹⁵. ACHIEVE included group and individual weight-management and group exercise sessions, which was led by trained study interventionists. Given the obesity epidemic in persons with SMI, there is an urgent need to “scale-up” or expand ACHIEVE to similar settings and populations as those included in the RCT, which we posited could be accomplished by enabling the psychiatric rehabilitation program staff to deliver the sessions¹⁶. Using the Enhanced Replicating Effective Programs Framework for translating evidence-based interventions into community settings¹⁷, our scale-up strategy considers this model’s three stages: pre-implementation, implementation, and dissemination.

As part of the pre-implementation stage, we adapted the format of the original intervention to increase ease of adoption and sustained implementation of ACHIEVE by program staff in these community-based programs. (IRB00194122). We retained the core components, but modified the curriculum schedule (e.g., combined exercise and weight management group sessions) and enhanced the delivery format (e.g., video-assisted content) to support efficient, staff-led delivery. We pilot tested this adapted curriculum (ACHIEVE-D) where a trained study interventionist implemented 2 months of programming at a community-based psychiatric rehabilitation program¹⁸, and we then further refined the adapted curriculum based on feedback from program staff and participating individuals with SMI.

In the implementation stage, the objective of this study is to develop and test innovative interventions to give community-based psychiatric rehabilitation program staff the knowledge, self-efficacy, and skills to deliver the adapted ACHIEVE curriculum (ACHIEVE-D) with high fidelity. Training of the ACHIEVE study interventionists required significant in-person initial and ongoing training, as well as performance feedback with particular emphasis on motivational interviewing skills^{14,15}. Time and other logistical constraints prevent community-based psychiatric rehabilitation program staff from participating in such intensive training. By leveraging novel strategies that incorporate advances in training and feedback modalities (e.g., online training, virtual training environments), staff training could facilitate adoption and sustained implementation of the ACHIEVE curriculum. To prepare for dissemination, we will also determine the acceptability, appropriateness, and feasibility of both the ACHIEVE-D curriculum and the standard and enhanced strategies among coaches and program directors to direct further refinements of these products.

Strategies to increase implementation of an adapted, evidence-based weight management intervention in community mental health programs: The ACHIEVE Implementation and Dissemination Pilot Trial is an RCT testing the hypothesis that an enhanced intervention will be superior to a standard intervention in increasing program staff knowledge, self-efficacy, and skill to deliver the adapted ACHIEVE curriculum with high fidelity. We will randomly assign 10 community-based psychiatric rehabilitation programs in Maryland to the standard or enhanced intervention for ACHIEVE, and we will enroll 2 staff members per program to participate as coaches. A peer leader will assist them. The standard intervention will combine real-time onboarding training via Zoom, ongoing online training, and online avatar-assisted motivational interviewing practice^{19,20} for coaches, as well as organizational strategy meetings to garner the leadership support for ACHIEVE implementation²¹. The enhanced intervention will include all standard strategies and will add performance

coaching for ACHIEVE staff coaches. All enrolled coaches will deliver the adapted ACHIEVE curriculum to consumers with SMI at each study site. We propose the following Aims:

2. SPECIFIC AIMS

Primary Aim: Conduct a pilot randomized clinical trial testing two implementation interventions designed to support delivery of ACHIEVE-D at community-based psychiatric rehabilitation programs.

H1.1. Both the standard and enhanced interventions will increase knowledge of and self-efficacy to deliver ACHIEVE-D, and result in high-fidelity delivery of ACHIEVE-D.

H1.2 Compared to the standard intervention, the enhanced version will lead to greater knowledge, self-efficacy, and ACHIEVE-D fidelity.

Secondary Aims:

1. Assess the acceptability, appropriateness, and feasibility of the adapted ACHIEVE curriculum to coaches, peer leaders, program directors and other staff.
2. Assess consumer outcomes of self-reported diet and physical activity, weight, attendance and satisfaction.

This study will lead to a refined intervention that will contribute to the future development of a certified ACHIEVE-D training program for mental health staff and peers, and thus facilitate future widespread dissemination of an evidence-based behavioral weight-loss program for individuals with SMI.

3. BACKGROUND & SIGNIFICANCE

Public health burden of CVD, obesity, and other CVD risk factors in persons with SMI

CVD is the leading cause of preventable death among persons with SMI⁴⁻¹⁰, and this population has high prevalence of CVD and CVD risk factors²²⁻²⁶. Notably, obesity is extremely common¹⁻³. For example, 60% of women with SMI have obesity^{2,27,28} as compared to 41% of women in the general population²⁹.

Factors that contribute to obesity in individuals with SMI

Several factors contribute to the high obesity prevalence. First, the vast majority of individuals with SMI take at least one long-term psychotropic medication, and these drugs promote weight gain due to increased appetite along with metabolic abnormalities such as elevated glucose and lipids³⁰⁻³⁶. A shared decision-making process that provides patients with the expected weight and metabolic effects of these medications has been the recommended strategy to clinicians to make an informed decision about choice³⁷. Unfortunately, initial selection of or changes to a weight-neutral alternative medication may not be an option for many individuals with SMI; therefore, medications are unlikely to be a modifiable risk factor.

Second, diet and physical activity are typically poor in this population. Studies of individuals with SMI demonstrate high calorie and fat intake, as well as low intake of fruit and vegetables³⁸⁻⁴³. Physical activity levels are low in this population⁴⁴⁻⁴⁸. For example, persons with SMI report 50% higher leisure time inactivity than the general population⁴⁵, and an accelerometry study showed only 4% of individuals with SMI met recommended moderate to vigorous physical activity in bouts of ≥ 10 minutes⁴⁸. These lifestyle habits also contribute to obesity and CVD risk among individuals with SMI, and unlike psychotropic medications, represent a modifiable CVD risk factor.

Challenge of behavioral weight-loss interventions among persons with SMI

In general populations, behavioral weight-loss interventions have been demonstrated to improve CVD risk by reducing blood pressure and glucose, as well as improving lipid profiles¹¹. Behavioral interventions promoting healthy diet, exercise, and weight loss are critically needed, but must be adapted to challenges particularly to the SMI population. In particular, memory impairment, limited executive function, and residual psychiatric symptoms^{12,13}.

A successful behavioral weight-loss intervention tested in an RCT within the SMI population

The NIMH-funded ACHIEVE trial was the first to demonstrate that an adapted behavioral intervention leads to clinically significant weight loss at 18 months among persons with SMI (mean 7 lbs. weight loss, net 3% loss)¹⁵. The magnitude of weight loss among individuals with SMI participating in ACHIEVE was similar to the

magnitude observed in efficacious weight-loss trials in general populations¹¹. The ACHIEVE intervention combined group and individual weight-management sessions with group exercise sessions delivered in community mental health programs^{14,15}. To address some of the noted challenges in this population^{12,13}, the intervention focused on repeated delivery of six key messages: avoid sugary drinks, avoid junk food, eat 5 servings of fruits/vegetables per day, portion control, smart snack habits, and regular physical activity. The ACHIEVE intervention was predominantly delivered by trained study interventionists, though mental health program staff delivered some video-assisted group exercise sessions^{14,15}. Given the obesity epidemic in persons with SMI, there is an urgent need to “scale-up” or expand ACHIEVE to similar settings and populations as those included in the RCT, which we posited could be accomplished by enabling the psychiatric rehabilitation program staff to deliver the sessions¹⁶. Using the Enhanced Replicating Effective Programs Framework for translating evidence-based interventions into community settings¹⁷, our scale-up strategy considers this model’s three stages: pre-implementation, implementation, and dissemination.

Scaling up ACHIEVE – pre-implementation stage

We have already completed the pre-implementation stage, during which we adapted the format of the original intervention to increase ease of adoption and sustained implementation of ACHIEVE by program staff in these community-based programs. (IRB00194122). To realize the full public health potential of ACHIEVE, the curriculum needed to be modified for delivery by community mental health staff¹⁶. We retained the core components, but modified the curriculum schedule (e.g., combined exercise and weight management group sessions) and enhanced the delivery format (e.g., video-assisted content) to support efficient, staff-led delivery. We pilot tested this adapted curriculum where a trained study interventionist implemented 2 months of programming at a community-based psychiatric rehabilitation program¹⁸, and we then further refined the adapted curriculum based on feedback from program staff and participating individuals with SMI. First, we defined the role for a peer leader within ACHIEVE, where a consumer would be recruited to serve as the peer leader from the group of participating consumers and the duties would include encouraging other enrolled consumers to attend ACHIEVE groups, actively participate in the group exercise sessions to act as a role model, as well as assist the ACHIEVE coach with set up and management of curriculum materials. Second, we identified the need for an assessment of readiness to make the necessary lifestyle behavior changes among consumers to ensure that we enroll individuals who are at an appropriate stage of change to engage in the intensive ACHIEVE curriculum.

In addition, we developed implementation strategies such as organizational strategy meetings with program directors and coaches to support the adoption of ACHIEVE in community-based psychiatric rehabilitation programs. We also refined procedures and assessment measures for grading coach fidelity to ACHIEVE, as well as adapted measures to assess acceptability, appropriateness, and feasibility.

Scaling up ACHIEVE – implementation and dissemination stages

The ACHIEVE Implementation and Dissemination Pilot Trial represents the next stages of the Enhanced Replicating Effective Programs Framework – implementation and dissemination¹⁷, which has a particular focus on testing innovative interventions to enable psychiatric rehabilitation program staff to deliver ACHIEVE-D.

[figure not shown]
The ACHIEVE trial interventionists, who all had bachelor’s or master’s degrees in health-related fields, required significant in-person initial and ongoing training on intervention content and motivational interviewing (MI)^{14,15}. MI is an evidence-based patient-centered communication method shown to help people make positive diet and exercise changes⁴⁹⁻⁵¹, and considered a key aspect of ACHIEVE. Traditional MI training includes two days of in-person training, followed by repeated post-training feedback and coaching by a master trainer. While the community-based psychiatric rehabilitation program staff have valuable experience working with people with SMI, they typically have different educational backgrounds and less experience with lifestyle content as well as MI communication skills. In real-world community mental health settings, time constraints prevent most program staff from participating in the intensive training used among ACHIEVE trial interventionists. Therefore, new strategies need to be developed that incorporate advances in training modalities (e.g. online training, virtual training environments) to enable psychiatric rehabilitation program staff to deliver ACHIEVE-D. Given that training alone is often insufficient to increase wide-spread adoption of new evidence-based interventions⁵²⁻⁵⁵, the ACHIEVE-D curriculum will be supplemented with additional implementation strategies (e.g.,

organizational strategy meetings with program directors and coaches, peer leader identification and training to aid coach) to support future implementation and dissemination of ACHIEVE-D in community mental health settings. Unless effective interventions like ACHIEVE are translated into real-world settings, obesity and CVD disparities among the population with SMI will likely persist or even worsen.

4. DESIGN SUMMARY

The core design is a randomized, two-arm, parallel, pilot clinical trial where 10 psychiatric rehabilitation program sites will be randomized to a 6-month standard or enhanced intervention. This trial will recruit and enroll participants at each site – staff, peer leaders, and mental health consumers, (Figure 1). The primary outcome variables will be coaches' knowledge, self-efficacy, and fidelity to the ACHIEVE curriculum.

Figure 1. Study Populations with Corresponding Activities and Outcomes for Each Site

We estimate up to 280 mental health organization staff and peer leaders will participate in data collection including program directors, coaches, and other psychiatric rehabilitation program staff. Two coaches and one peer leader per study site will be randomized to the standard or enhanced intervention. Up to 120 mental health consumers across all sites will be enrolled, and all will receive group weight-management sessions delivered by the trained coaches at their site.

The ACHIEVE-D curriculum is designed to fit into and will be part of the regular psychiatric rehabilitation programming that is already being conducted.

Randomized groups:

Standard intervention: At those sites assigned to the standard group, two staff and one peer will receive training and approximately 8-12 consumers with SMI will participate in the ACHIEVE weight loss program. The standard intervention will combine onboarding training, ongoing online training, and online avatar-assisted motivational interviewing practice^{19,20} for all coaches, as well as organizational strategy meetings to garner the leadership support for ACHIEVE implementation²¹.

Enhanced intervention: At those sites assigned to the enhanced group, the implementation intervention will include all standard strategies and will add performance coaching for the coaches.

Trainings and meetings will be remote during the COVID-19 pandemic.

We outline the eligibility criteria sites in Section 5. Then, we describe the eligibility criteria as well as data collection and measurements for each study population separately in Sections 6-8.

5. SITE ELIGIBILITY

We will recruit approximately 10 community psychiatric rehabilitation programs across Maryland as study sites. (Table 1).

In general, sites will need 1) to be an adult psychiatric rehabilitation program. 2) Willing to implement the ACHIEVE curriculum; 3) Willing to support 2 staff members being trained as coaches and implementing the curriculum; 4) Willing to have a peer leader assist.

Table 1. Criteria for study sites

• Adult psychiatric rehabilitation program with willingness to implement the ACHIEVE curriculum at least one time per week for 6 months.

• Willingness to support 2 staff members to be trained and serve as ACHIEVE coaches
○ Training: ~16 hours of onboard training; ~2-4 hours per month of additional online training; ~1.5 hours per month for performance coaching if site is randomized to the enhanced training intervention arm○ Coach duties: Lead at least one (and up to three) 1-hour sessions per week of the ACHIEVE curriculum to enrolled consumers

• Willingness to support a peer leader to assist with the curriculum.
○ Training: ~16 hours of onboard training; ~2-4 hours per month of additional online training○ Peer leader duties: Assist staff coaches

• Organizational leaders and staff to participate in organizational strategy meetings with the study team. ~1 meeting every month

• Anticipated ability for study team to recruit consumers to participate in the ACHIEVE curriculum

• Ability for study staff to collect data from coaches, consumer participants, and other staff members

6. STUDY POPULATION: COACHES AND PEER LEADERS

6.1 Eligibility criteria

To be eligible to be a coach, the person must be age 18 or older and a staff member at a psychiatric rehabilitation program, as well as be willing to do the following: complete all training activities as part of the ACHIEVE intervention, deliver all components of the ACHIEVE curriculum to consumers at the program, work with a peer leader as part of the ACHIEVE curriculum, and complete data collection procedures as a study participant. We will exclude staff who plan on leaving their position or taking a leave of absence from the psychiatric rehabilitation program within the next 12 months.

For peer leaders, we will seek individuals 18 years and older who are or are in training to become a Maryland Certified Peer Recovery Specialist, or who are mental health consumers with interest who the psychiatric rehabilitation program staff and study team believe would be a good fit (e.g., in a vocational program). The peer leader must be willing to do the following: complete training activities as part of the ACHIEVE intervention, deliver components of the ACHIEVE curriculum to consumers at the program, work with the staff coaches as part of the ACHIEVE curriculum, and complete data collection procedures. We will exclude peers who plan on leaving their position or taking a leave of absence within the next 12 months.

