6.2 Data collection procedures

Data collection is outlined in Table 2. Data collection for coaches and peer leaders will occur remotely via telephone or Zoom and/or online RedCap survey or delivered paper questionnaires. We will collect follow-up measures at 3 months and 6 months at completion of ACHIEVE curriculum.

Participant reimbursement for data collection for staff coach participants is estimated at \$160 total for completing all data collection. Participant reimbursement for data collection for peer leader participants includes \$75 for completing data collection, up to \$320 (\$20/hour) for participating in trainings and up to \$1500 (\$20/hour) per site for participating in delivery of the curriculum.

Table 2. Data Collection Schedule For Coaches and Peer Leaders

	Baseline	Follow-up		
		During	6M Post	6M Post project completion
Primary Outcomes				
ACHIEVE curriculum weight management knowledge	x		x	
ACHIEVE curriculum exercise knowledge	x		x	
Self-efficacy to deliver ACHIEVE curriculum	x		x	
ACHIEVE Fidelity Document Assessment Form		x		
ACHIEVE Fidelity Video Assessment Form		x		
Other Measures				
Demographics & prior training	x			
Attitudes towards individuals with obesity	x			
Calculated BMI	x		x	
CARDIA/EARLY Q – sedentary behavior	x		x	
Block Dietary Fat Q	x		x	
Block Dietary Fruit/Vegetable Q	x		x	
EARLY Eating Away from Home Q	x		x	
EARLY SSB Consumption Q	x		x	
Perceived Stress Scale	x		x	
Self-Efficacy recall			x	
Beliefs about Motivational Interviewing	x	x	x	
Importance and Confidence of Using MI	x	x	x	
Avatar MI Performance Measurements	x	x	x	
Avatar Motivational Interviewing (MI) satisfaction survey			x	
Perceived Usefulness (motivational interviewing avatar platform)			x	
Fidelity to Motivational Interviewing	x	x	x	
Implementation Measures				
Acceptability of training	x		x	
Feasibility of training	x		x	
Appropriateness of training	x		x	
Motivation for implementation	x		x	
Implementation Climate	x			
Qualitative Assessment				
Focus Group Interviews			x	x

Abbreviations: BMI – body mass index; Q – questionnaire; SSB – sugar-sweetened beverage.

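### A peer leader who is not an enrolled consumer may exercise in study sessions without the Section 7.2 pre-exercise screen

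*Combined protocol and SAP*

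**What the plan says.** The protocol describes the peer leader in several places.

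- **Section 3 (pre-implementation stage).** After the pilot work, the role was defined so that "a consumer would be recruited to serve as the peer leader from the group of participating consumers". One of the duties was to "actively participate in the group exercise sessions to act as a role model".
- **Section 5, Table 1.** The only duty listed is "Peer leader duties: Assist staff coaches".
- **Section 6.1.** A peer leader must be an adult and either a certified peer recovery specialist, in training to become one, or one of those "who are mental health consumers with interest who the psychiatric rehabilitation program staff and study team believe would be a good fit". The only exclusion is a planned departure or leave within 12 months.
- **Section 6.2 and Table 2.** "Data collection for coaches and peer leaders will occur remotely via telephone or Zoom", or by online or paper questionnaire. The schedule has no PAR-Q, medical history, medication, blood pressure or medical-events row. Calculated BMI is the only physical measure.
- **Sections 11 and 11.1.** Peer leaders assist coaches, and may lead, co-lead or facilitate separate 20-minute moderate-intensity video exercise classes.

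The pre-exercise screen (modified 2018 PAR-Q, medical-condition checklist, blood pressure, and physician contact where needed) is set out in Section 7.2 for consumers. Section 7.3 and Table 5 also tie it to consumers, and Section 15 limits the orthopedic and rheumatologic screen to them.

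**The concern.** Under the Section 3 model the peer leader who exercises is a participating consumer, so the consumer screen would apply. Section 6.1 widens the source of peer leaders but does not carry that screen with it. Some peer leaders may themselves be consumers with serious mental illness, of whom Section 3 says "this population has high prevalence of CVD and CVD risk factors".

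Table 3 would keep a consumer out of the program after a cardiovascular event in the last 6 months, or for insulin-dependent diabetes or inability to walk unassisted. Nothing in Section 6.1 stops the same person from serving as peer leader in the same class. What is at stake is the safety of a few individuals. The primary outcomes, the randomization and the Section 13 models are untouched.

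**Working it through.** The protocol gives no figure on this point, so the main check sets the sections side by side. Arithmetic serves only to size the issue.

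**Step 1: does the consumer screen reach peer leaders by another route?** Section 4 says that eligibility, data collection and measurements are described separately for each population in Sections 6 to 8, so Section 7 rules do not carry over to Section 6. Section 14 says eligibility is determined through each population's own baseline data collection. For peer leaders that is Table 2, which has no screening item. A peer leader who is also an enrolled consumer is screened as a consumer; one who is not has no defined screen.

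**Step 2: does the peer leader exercise?**

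| Where | Source of peer leader | Role in exercise |
|---|---|---|
| Section 3 | Participating consumers | Takes an active part |
| Table 1, Section 6.1 | Peer specialists or interested consumers; enrolment not required | Assists coaches; delivers components |
| Sections 11, 11.1 | Not restated | Leads, co-leads or facilitates |

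Only Section 3 says that the peer leader exercises. Sections 11 and 11.1 neither require nor rule it out. The plan therefore permits an unscreened peer leader to exercise but does not prescribe it.

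**Step 3: how many people?** Section 4 gives 10 sites and one peer leader per site: 10 × 1 = 10. The number who are not also enrolled consumers is not stated, so the range is 0 to about 10.

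**Step 4: how much exercise in ACHIEVE groups?** Exhibit 1 gives 30 minutes of weight management, 20 minutes of exercise and a 10-minute weigh-in: 30 + 20 + 10 = 60 minutes per session. I take six months as 26 weeks.

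- Peer leader only facilitates, or the site holds no group exercise: 0 hours.
- One session a week: 26 × 20 = 520 minutes, about 8.7 hours.
- Two sessions a week: 26 × 2 × 20 = 1,040 minutes, about 17.3 hours.
- Pay cap: Section 6.2 allows up to $1500 at $20 an hour "per site for participating in delivery of the curriculum". That is 1500 / 20 = 75 hours, or 75 one-hour sessions, just below the 26 × 3 = 78 sessions of a three-a-week schedule. Exercise time is 75 × 20 = 1,500 minutes = 25 hours.

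Every non-zero figure assumes exercise at every session and a peer leader who exercises each time. The 25-hour figure also assumes no attendance beyond paid hours. The separate virtual classes are not counted, because their frequency is not stated.

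**The case against.** The strongest reply is that the hazard joins two different role descriptions. The exercise duty comes from Section 3, which is background on the pilot refinements and recruits from participating consumers. The wider source comes from Section 6.1, where the duties are to assist and to deliver components. No single section describes an unscreened peer leader who exercises. This stands as a limit: a reader might infer that the plan sends unscreened peer leaders to exercise, and the text does not support that. It does not dispose of the point. The Section 3 duty is never withdrawn, the other refinement listed beside it (a readiness assessment for consumers) is carried into the trial in Sections 7.2 and 7.3, and co-leading an exercise video leaves room for exercising.

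The second reply is that general safeguards exist. Section 16 commits to American College of Sports Medicine guidance and to supervision of exercise sessions without naming a population. Section 11.1 has a study team member watch the virtual classes. Section 14 provides round-the-clock clinician cover. Section 6.1 requires a judgment of fit for interested consumers. These reduce the risk, but none is a defined check for a contraindication before exercise starts.

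A reader might also infer that peer leaders have no six-month event follow-up. That goes too far. Section 15 words the surveillance for participants, and Section 6.2 calls peer leaders participants. On the other side, Table 2 has no such row, and Section 14 places its safety monitoring under a heading for consumers. Coverage is unclear rather than absent.

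Staff coaches must "deliver all components of the ACHIEVE curriculum to consumers at the program" and have no screen either. No text gives them an active part in the exercise, so the point is not extended to them.

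**Conclusion.** The point holds in conditional form. Section 6.1 admits peer leaders who need not be screened consumers, sets no health criterion, and has no exercise screen in Table 2. If such a person exercises in study sessions, the plan lets it happen without the Section 7.2 screen.

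The size is small: 0 to about 10 people. The 25-hour figure in ACHIEVE groups is a ceiling and should not be read as a typical exposure. In-person group exercise depends on each site's COVID rules, and one group a week is the minimum. The proportion of peer leaders with a relevant condition is not given, so no event rate can be derived. No outcome or analysis changes. I would class this as a minor, cheap improvement to individual safety.

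**What to change.** In Section 6.1 and Table 2, state that any peer leader who is not an enrolled consumer participant and who will exercise in study sessions completes the existing modified 2018 PAR-Q and medical-condition checklist at baseline, remotely. Blood pressure, physician contact and study clinician review follow only if a form is flagged. A peer leader who does not complete the forms, or whom the clinician does not clear, facilitates without exercising. State also that the six-month event surveillance in Section 15 covers these peer leaders.

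The cost is at most about 10 × 2 = 20 short baseline forms, which fits the remote collection already planned. The downsides are real but small. A little extra health information is asked of people in a paid role, the clinician has occasional forms to review, and raised blood pressure in an unflagged peer leader would be missed. An occasional peer leader would be limited to non-exercise duties. If the sponsor intends that non-enrolled peer leaders never exercise, one sentence in Section 6.1 saying so would replace the forms.
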